Outpatients (n=160) with mild to severe TBI were randomly assigned to either a treatment (RAI) or wait list control (WLC) group. Treatment was delivered in seven one-hour sessions with outcome measurement pre- and post-treatment, and three months after treatment completion.

Outcome measures included the Connor-Davidson Resilience Scale (CD-RISC),⁹⁷ Mayo Portland Adaptability Inventory-4 (MPAI-4),¹⁶⁴ Brief Symptom Inventory-18 (BSI-18),¹⁶⁵ and 13 Item Stress Test.¹⁶² As indicated in the table that follows, treatment group participants showed improvement in outcomes, whereas controls did not. At three months post-treatment, improvements were maintained relative to pre-treatment.

Outcome	Group	Baseline	Post-treatment	Follow-up
	_	Mean (SD)	Mean (SD)	Mean (SD)
CD-RISC	RAI	21.1 (8.1)	28.4 (6.9)	25.5 (7.8)
	WLC	23.4 (9.0)	23.7 (8.1)	-
MPAI-4: Adjustment Index	RAI	55.4 (9.1)	51.2 (9.5)	50.7 (10.0)
	WLC	55.8 (10.5)	54.5 (9.2)	-
MPAI-4: Ability Index	RAI	55.0 (9.7)	51.0 (8.3)	50.7 (9.5)
	WLC	53.5 (10.8)	54.2 (9.5)	-
BSI-18	RAI	63.8 (11.7)	57.2 (10.6)	58.7 (10.4)
	WLC	64.1 (10.7)	64.0 (9.4)	-
Stress	RAI	6.7 (3.3)	4.5 (3.4)	5.0 (3.1)
	WLC	6.5 (3.5)	6.0 (3.3)	-

A linear mixed-effect model was used to model each outcome, with the time point (baseline, post-treatment, 3-month follow-up), treatment, and interaction as explanatory variables. Each of these models was also adjusted for education level, time postinjury, and injury severity. The table below displays between group outcome differences from baseline to post-treatment, as well as changes from baseline to 3-month follow-up for the RAI group.

	RAI – WLC at Post-treatment		3-Month Follow-up – Baseline for RAI	
Outcome	Difference (95% CI)	Р	Difference (95% CI)	Р
CD-RISC	6.70 (4.96, 8.43)	< 0.001	4.36 (2.42, 6.30)	< 0.001
MPAI-4: Adjustment	-2.48 (-4.55, -0.41)	0.019	-4.61 (-6.95, -2.27)	< 0.001
MPAI-4: Ability	-3.75 (-5.85, -1.65)	< 0.001	-4.05 (-6.41, -1.69)	< 0.001
BSI-18	-6.51 (-8.73, -4.30)	< 0.001	-5.01 (-7.52, -2.50)	< 0.001
Stress	-1.50 (-2.23, -0.77)	< 0.001	-1.60 (-2.40, -0.81)	< 0.001

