Additional quality control procedures will be implemented for booster sessions with each

therapist. As indicated in the Intervention section, booster sessions are person-centered and thereby

highly individualized. Audio-recordings will be made for the three booster sessions and reviewed

with [name] to ensure that key areas are covered as outlined in the manual. Every six months

thereafter, quality control procedures will be repeated.

Data collection procedures: Demographic, injury severity, and history information will be

collected at baseline using TBIMS standard procedures. For RAI and RAI+ participants, outcome

measures will be obtained prior to treatment (baseline) and following completion of the RAI.

Outcome measures for RAI+ participants will be obtained at the start and completion of the booster,

and six months following completion of the booster sessions. Measures for RAI participants will be

obtained at three, four, and nine months post-RAI treatment. Data collection will occur within the

same timeframe for both RAI and RAI+ participants as outlined in the figure that follows.

Project timeline: The major activities for the research project are sequentially delineated in the

Plan of Operation section.

E. Data Analysis

Descriptive statistics (e.g., means, standard deviations, proportions) will be calculated for all

measures at designated time intervals. Analyses will be performed using the university licensed

statistical program SAS v.9.3 (© 2002- 2010; SAS Institute Inc.; Cary, NC). The following table

provides a description of major statistical analysis procedures, emphasizing priority areas related to

research hypotheses. Information is provided regarding statistical hypotheses, statistical methods,

power analysis and sample size estimates. Analyses evaluating the RAI+ are based on the intent-to-

treat principle if drop-out is assumed as missing at random or missing completely at random.

Hypothesis 1 – Primary: Participants receiving the booster (RAI+ group) will report higher levels of resilience in comparison to individuals in the standard RAI group.

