Statistical Methods: A linear mixed-effects model will be used to model the CD-RISC scores over time for the RAI and RAI+ groups. The model will include fixed-effects for time at RAI+Booster initiation, conclusion, and long-term follow-up (e.g. 5, 6, and 11 months), group (RAI or RAI+) and the interaction between group and time. The model will also adjust for fixed-effects for injury severity, time postinjury, and education. Within-subject correlations in the CD-RISC scores over time will be modeled using a spatial power covariance pattern structure. Specific contrast statements will be used to test for a difference in the CD-RISC change scores between the treatment groups at both RAI+Booster initiation and conclusion as well as RAI+Booster initiation and long-term follow-up at a significance level of .05.

Power Analysis: Data obtained by our group indicated that the mean CD-RISC increased from a baseline value of 21.1 units to a mean of 28.4 units post-treatment (Difference=7.3), followed by a decline to 25.5 at the 3-month follow-up (Difference=2.9), with a standard deviation (SD) of the change score equal to 5.0. Considering a conservative SD of 6.0, this study will require 138 participants (n=69 per group) using a two-sample t-test performed at the 0.05 significance level to achieve 80% power. This effect translates to an effect size d=2.9/6.0=0.48, which is typically considered a moderate effect size.

Hypothesis 2: Participants in the RAI+ group will show better adjustment and lower levels of emotional distress as compared to persons in the standard RAI group.

Statistical Methods: Separate mixed-effects models, similar to that outlined in the methods for Hypothesis 1, will be used to model the responses for the MPAI-4 Adjustment Index and the BSI-18 GSI scores over time for each group. Specific contrast statements will be used to test the hypotheses of interest, each assuming a significance level of .05. Using a similar 40% decrease between the baseline to post-treatment values observed in our pilot study, we would expect the RAI+ to ameliorate declines in the MPAI-4 Adjustment and BSI-18 GSI scores by 1.7 and 2.6 points, respectively. Considering a conservative SD of 7.0, the 138 participants enrolled would provide power of 29% and 58% for the two outcomes, if analyzed by a two-sample t-test at the 0.05 level.

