Hypothesis 3: Participants in the RAI+ group will report greater abilities in the areas of problem solving, communication, and stress management relative to persons in the standard RAI group. **Statistical Methods:** Two additional mixed-effect models, similar to the first three, will be used to

model the MPAI-4 Ability scores and the 13-Item Stress Test scores over time for each group. Again, a specific contrast statement will be used to test the hypothesis of interest at a significance level of α = .05. In a similar fashion to Hypothesis 2, a 40% decrease between the observed baseline to post-treatment values yields differences of 1.6 and 0.9 for the MPAI-4 Ability Index and the 13-Item Stress Test. Considering a conservative SD of 7.0 and 2.0, respectively, the 138 participants enrolled would provide power of 27% and 75% for the two outcomes, if analyzed by a two-sample t-test at the 0.05 level.

Hypothesis 4 (exploratory): A participant's demographic, lifestyle, injury, and treatment response information will be predictive of maintenance ability.

Statistical Methods: Separate linear regression models will be used to determine the relationship between each of the demographic, lifestyle, injury, and initial RAI response characteristics and both the change in the 5 and 6 month CD-RISC scores, as well as the change in the 5 and 11 month CD-RISC scores. Assuming 69 participants in the RAI group complete the study and 8 predictor variables are in the linear regression model, this analysis will have 80% power to detect effect sizes of f^2 =0.12, which is considered a moderate effect size.

Power analyses relating to the primary hypothesis indicate minimum group sizes of 69 participants.

If we allow for a maximum of 10% attrition, then an additional 8 individuals per treatment group

(16 individuals total) should be recruited (138/(1-0.1)-138 = 15.3) for a total sample size of 154.

F. Feasibility F1. Project Staff

Personnel effort levels are based on thorough consideration of our prior experience conducting

similar projects. Following is information on responsibilities of personnel allocating >5% effort:

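### The secondary powers for Hypotheses 2 and 3 (29%, 58%, 27%, 75%) borrow the CD-RISC's 40% loss of gain, although the pilot table gives each outcome's own loss, which is smaller or absent

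*Combined protocol and SAP*

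**What the plan says.** All places are in the grant application part of the combined protocol and SAP, section III (Research Activities), unless noted.

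- **E. Data Analysis, Hypothesis 1.** The power calculation uses the pilot course of the CD-RISC itself: a gain of 7.3 points, then a loss of 2.9 by 3 months. With an SD of 6.0 this gives 69 per group for 80% power.
- **Hypothesis 2.** "Using a similar 40% decrease between the baseline to post-treatment values observed in our pilot study", the plan says, "we would expect the RAI+ to ameliorate declines in the MPAI-4 Adjustment and BSI-18 GSI scores by 1.7 and 2.6 points". With an SD of 7.0 and 138 participants it states power of 29% and 58%.
- **Hypothesis 3.** By the same route, "a 40% decrease between the observed baseline to post-treatment values yields differences of 1.6 and 0.9 for the MPAI-4 Ability Index" and the 13 Item Stress Test respectively. With SDs of 7.0 and 2.0 it states power of 27% and 75%.
- **Literature review, account of the earlier VCU trial.** The first results table gives RAI-arm means at baseline, post-treatment and 3-month follow-up for all five outcomes. The second gives adjusted changes from baseline to 3 months with 95% intervals.
- **IRB form, Study Population, sample size justification.** The attrition allowance changes, but 69 per group is kept and no new secondary power is given.

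**The concern.** The phrase about values observed in the pilot can be read as saying that a 40% loss was seen in these outcomes. The pilot table shows that fraction only for the CD-RISC. For BSI-18 and Stress the loss is roughly half as large. Both MPAI-4 indices went on improving slightly after treatment, so the worsening in Adjustment that RAI+ is meant to offset does not appear in the pilot means.

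The powers for the MPAI-4 indices are openly low, and nobody is likely to lean on them. The Stress figure (75%) looks close to adequate and the BSI-18 figure (58%) moderate. A reader might use those two to treat a non-significant secondary result as informative.

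**Working it through.** **1. Reproduce the stated powers.** Two-sample t-test, alpha 0.05, n = 69 per group, noncentrality = (difference/SD) × sqrt(69/2). The plan does not state sidedness; two-sided reproduces its figures, whereas one-sided would give 41%, 70%, 38% and 84%.

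| Outcome | Pilot gain | 40% of gain | Plan's difference | SD | Power, recomputed | Power, stated |
|---|---|---|---|---|---|---|
| MPAI-4 Adjustment | 55.4 - 51.2 = 4.2 | 1.68 | 1.7 | 7.0 | 29.4% | 29% |
| BSI-18 | 63.8 - 57.2 = 6.6 | 2.64 | 2.6 | 7.0 | 58.2% | 58% |
| MPAI-4 Ability | 55.0 - 51.0 = 4.0 | 1.60 | 1.6 | 7.0 | 26.6% | 27% |
| Stress | 6.7 - 4.5 = 2.2 | 0.88 | 0.9 | 2.0 | 74.7% | 75% |

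The arithmetic is right.

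**2. Source of the 40%.** CD-RISC: (28.4 - 25.5)/(28.4 - 21.1) = 2.9/7.3 = 39.7%. The fourth column follows when this fraction, rounded to 40%, is applied to each other outcome's gain.

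**3. Each outcome's own pilot loss.** Higher scores are worse on these four scales, so loss = 3-month mean minus post-treatment mean.

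| Outcome | Post-treatment | 3 months | Loss | Share of gain |
|---|---|---|---|---|
| BSI-18 | 57.2 | 58.7 | 1.5 | 1.5/6.6 = 23% |
| Stress | 4.5 | 5.0 | 0.5 | 0.5/2.2 = 23% |
| MPAI-4 Adjustment | 51.2 | 50.7 | -0.5 | no loss |
| MPAI-4 Ability | 51.0 | 50.7 | -0.3 | no loss |

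Rounding of the printed means does not close the gap. It moves the BSI-18 loss only between 1.4 and 1.6, and the Stress loss between 0.4 and 0.6. This checks rounding and is not a measure of uncertainty.

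**4. Power with Hypothesis 1's method, that is, the outcome's own pilot loss.** Same formula, n and SDs:
- BSI-18: 1.5/7.0 = 0.214, power about 24% (58% stated).
- Stress: 0.5/2.0 = 0.25, power about 31% (75% stated).
- MPAI-4 indices: no observed mean loss, so no figure can be formed this way.

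**5. Precision of the pilot.** The plan gives no interval for the loss itself. A rough one is the raw gain, taken as fixed, minus the limits of the adjusted improvement from baseline to 3 months. This mixes raw and adjusted values.
- BSI-18: 6.6 - 7.52 = -0.92 to 6.6 - 2.50 = 4.10; the assumed 2.6 lies inside.
- Stress: 2.2 - 2.40 = -0.20 to 2.2 - 0.81 = 1.39; 0.9 lies inside.
- Adjustment: 4.2 - 6.95 = -2.75 to 4.2 - 2.27 = 1.93; 1.7 lies inside.
- Ability: 4.0 - 6.41 = -2.41 to 4.0 - 1.69 = 2.31; 1.6 lies inside.

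The upper ends for BSI-18 and Stress would give power of about 93% and 98%; the lower ends mean no loss at all.

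**The case against.** The strongest reply is that the pilot does not contradict the assumption. All four assumed differences lie inside the implied intervals, and a single retention fraction across outcomes is a recognisable planning choice whose source can be worked out from the Hypothesis 1 text. The pilot loss also covers the wrong window. It runs from 0 to 3 months after treatment, while the trial's contrasts start at booster initiation, with RAI-arm measures "obtained at three, four, and nine months post-RAI treatment". An outcome's own 0-3 month loss is therefore a proxy too. The boosters are also meant to deal with new difficulties (D3. Intervention), so their effect need not equal the decay seen in the pilot. Finally, the figures are offered only as two-sample t-test approximations to a covariate-adjusted mixed model, for secondary hypotheses that all fall below 80%.

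Most of this stands, and it rules out three stronger readings. A reader might infer that true power is 24% and 31%; the pilot is too imprecise, and stops too early, to show that. A reader might infer that the MPAI-4 effects are zero and that 29% and 27% should be deleted; a mean without loss in one pilot does not show a zero effect, and the figures remain valid as conditional statements. A reader might infer that the sample size is wrong; it rests on the CD-RISC alone.

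The reply does not remove the inconsistency. The window and precision limits apply equally to the borrowed 40%, which is also a 0-3 month fraction, from a different scale. Hypothesis 2 justifies its differences as offsetting declines rather than as new gains, and Hypothesis 1 uses its outcome's own loss.

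**Conclusion.** The concern holds as a matter of how the secondary powers are supported and described. They are computed correctly from a fraction that the plan's own pilot means show for the CD-RISC but not for the four outcomes concerned. Applying Hypothesis 1's method changes BSI-18 from 58% to about 24% and Stress from 75% to about 31%, and leaves no observed decline behind the two MPAI-4 figures.

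These values assume 69 analysed per group, a two-sided 0.05 t-test, the plan's SDs (7.0 and 2.0) and unadjusted RAI-arm means. They show how sensitive the stated powers are to the input; they are not estimates of the true power. Severity is minor.

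**What to change.** Amend the wording under Hypotheses 2 and 3 in E. Data Analysis:

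1. State that the 40% is the CD-RISC loss of gain (2.9/7.3), and label 29%, 58%, 27% and 75% as conditional on that fraction applying to each outcome.
2. Add the pilot-based values. *Hypothesis 2:* BSI-18 GSI lost 1.5 of its 6.6-point gain by 3 months; at SD 7.0 and 69 per group this point estimate gives power of about 24%. MPAI-4 Adjustment showed no mean loss, so a decline for RAI+ to offset is an assumption. *Hypothesis 3:* the Stress Test lost 0.5 of 2.2 points; at SD 2.0 this gives about 31%. MPAI-4 Ability showed no mean loss, so the same caution applies.
3. Add to both: the pilot intervals are wide (implied losses of about -0.9 to 4.1 for BSI-18 and -0.2 to 1.4 for Stress, taking the raw gain as fixed), do not exclude a 40% loss, and give no information beyond 3 months after RAI.

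The MPAI-4 figures can stay once labelled. Bands that reflect only rounding of the printed means should not be shown next to the powers, because they would read as uncertainty ranges.

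The cost is a few sentences. Sample size, endpoints, tests and the primary hypothesis do not change; the description of secondary power becomes less favourable.

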Accrual rates may be lower than anticipated. Based on our past research success, we are confident in accrual rate estimates, particularly given commitments from the director of the Brain Injury Association of Virginia (BIAV) to facilitate recruitment. BIAV's Executive Director helped develop the treatment protocol, and has expressed optimism about the protocol's helpfulness. BIAV is in an excellent position to assist with recruitment because of their close, daily contacts with individuals with TBI and their families. Individuals often contact BIAV to request information about treatment alternatives and referral information. BIAV has agreed to help encourage participation in our research by dissemination of information in their newsletters and at conferences and workshops they sponsor. BIAV will also help disseminate information about the need for research participants to professionals and agencies. Advisory Board members, representing a variety of organizations (e.g., Department of Aging and Rehabilitative Services, Brain Injury Services, Mill House) and service providers (e.g., Tree of Life, Concussion Care Centre of Virginia), have also agreed to disseminate information about the project and the potential benefits of treatment (see Appendix C for letters of support).

Individuals with TBI may have difficulty completing measures because of difficulties with fatigue, vision, motor functioning, or other impairments. Failure to include participants with severe disabilities may also create a biased sample. Based on our experience, we anticipate that fewer than 10% of individuals who are three or more months postinjury will have significant difficulty completing the proposed measures. To reduce the likelihood of sample bias, we will invite participants to indicate whether they have difficulties and we will offer a variety of accommodations. Accommodations may include reading questionnaire items to the person or recording responses for them. A record will be kept of accommodations made for each person, allowing an evaluation of whether accommodations affected response patterns.

A number of participants may be unavailable for follow-up. The accrual numbers presented in this proposal are based upon a review of data collection rates in past studies conducted at VCU. Furthermore, with more than 25 years of experience conducting follow-up studies, we have developed an effective follow-up system. The cornerstones of the system include: (a) providing high quality clinical follow-up services; (b) maintaining up-to-date contact information; and (c) employing an efficient appointment reminder system. Our system employs a combination of in-person, written, and telephone reminders. Most of our studies have included annual follow-ups, and follow-up rates have ranged between 90-95%.

Participants may be involved in concurrent individual psychotherapy or support groups or may be taking psychotropic medications. Individuals will be eligible for this study regardless of concurrent mental health treatment. As a matter of ethical practice, psychiatric consultation will be offered to individuals requesting services or who appear to be in need. Information about concurrent treatment will be obtained during each assessment session and recorded for each participant. Statistical analysis will be implemented to assess the relationship between concurrent therapy participation and treatment (RAI) outcome.

Interventions may not be completed within the proposed timeframe. Ideally, the RAI will be completed in seven weeks. For RAI+ participants, ideally booster sessions begin three months after completion of the RAI and will be completed in three weeks. Unforeseen delays may arise (e.g., related

to illness, transportation) that may affect timelines. We have built in windows that allow a modicum of flexibility. We will record completion dates and statistically evaluate how outcome data are affected by deviation from prescribed time intervals.

G. Expected Beneficial Impact

- An effective intervention for survivors will improve psychological outcomes and provide a means of counteracting the adverse, far-reaching effects of reduced inpatient lengths of stay.
- Use of effective patient-focused intervention and outcome tracking will provide an empirical foundation for utilizing person-centered interventions.
- All systems of care have resource limitations. Improved understanding of effective skill building, support, and education strategies will help systems more efficiently allocate resources.
- Identifying the attributes of participants who are treatment-resistant will facilitate development of
 effective alternative treatments.
- Effective treatment to promote resilience and adjustment will reduce the adverse impact on family members who are often in a caregiving role.
- Providing empirically-based guidance to clinicians serving participants will enable them to deliver more effective and efficient services.
- Development of a structured, replicable intervention will allow treatment providers and advocacy
 organizations to provide services in more settings.
- New hypotheses will be generated for future treatment studies.
- Empirically-based research findings will provide a rationale for requiring third party payers to cover the cost of intervention services, previously dismissed as having uncertain efficacy.

Caregiver Resilience: A Longitudinal Investigation

Introduction and Review of Literature

Many persons with moderate to severe TBI require assistance from a caregiver for months or years postinjury.²¹⁵ A caregiver is an individual who provides help, support, guidance, or supervision to a person in need. Caregivers for persons with TBI are typically female and a parent or spouse of the survivor.^{216,217} While there is some evidence caregivers have positive feelings about their role,^{218,219} many report emotional distress,^{43,220-222} perceived burden^{44,223} and life dissatisfaction.²²⁴ One of the most widely-cited studies of caregiver distress was a TBIMS, multicenter prospective study.⁴³ Investigators found clinically significant rates of depression (19%), anxiety (18%), and somatic symptoms (24%), with one in ten caregivers exceeding the cut-offs on all three scales.

A shift in the field of psychology has led to a focus on the positive facets of postinjury adjustment, notably, resilience. Unfortunately, little is known about caregiver resilience after TBI. To date, only two studies have explored caregivers' postinjury resilience.^{67,68} Las Hayas and colleagues⁶⁷ found that Spanish caregivers' resilience was positively correlated with quality of life

and negatively correlated with perceived burden. However, the study aimed to describe the psychometric properties of a new resilience questionnaire, and caregivers' resilience levels were not described. Simpson and Jones⁶⁸ found that higher levels of resilience among Australian caregivers were associated with lower rates of negative affect and caregiver burden. Using Wagnild's criteria, the resilience level of Simpson's sample would be characterized as "moderately low to moderate."²²⁵ Las Hayas' and Simpson's studies are limited by small sample sizes and use of cross-sectional data from a single center.

Given the scarce literature on TBI caregivers, we examined studies of resilience among caregivers of persons with dementia. Although dementia differs from TBI in several important ways, caregivers of persons with dementia take on somewhat comparable caregiving roles, such as support of self-care, instrumental activities of daily living, cognitive functioning, and emotional well-being.²²⁶ Thus, findings from this literature can offer insight into resilience among TBI caregivers. In a Brazilian study of dementia caregivers, investigators found higher levels of resilience were related to lower levels of emotional distress. Caregiver resilience was unrelated to caregiver gender or patients' clinical or sociodemographic characteristics.²²⁷ Elnasseh and colleagues²²⁶ found that for Argentinian caregivers, higher levels of resilience were associated with empathy, optimism, and fewer family problems. Fitzpatrick and Vacha-Haase²²⁸ found that resilience was unrelated to marital satisfaction, but was related to self-efficacy. In a study of Alzheimer's caregivers, Wilks found that younger age and African-American ethnicity were associated with higher levels of resilience. Marital status, gender and relation to caregiver recipient were unrelated to resilience levels.²²⁹

In summary, the literature on resilience among caregivers of persons with dementia is generally characterized by small sample sizes^{227,228} and measurement at a single time point.²²⁶⁻²²⁸ Most studies did not fully describe resilience levels, leaving questions about the quality of caregivers' resilience unanswered. Of the two studies that did provide mean resilience values,^{227,229} resilience levels were considered to be moderate to moderately low based on general population norms.²²⁵ Nevertheless,

the evidence from both the literature on caregivers in TBI and dementia is clear – resilience is associated with emotional well-being^{67,68,227} and perceived burden.^{67,68}

A. Rationale: The Need for Research

Caregivers provide integral support to survivors, especially after hospital discharge. Concerns have been expressed that many survivors go home to family members who are ill-prepared to manage commonly encountered problems.²³⁰ Caregiving places a great burden on family members that is manifested in high rates of depression, anxiety, and somatic concerns.

Until recently, research on caregivers had focused on only the negative correlates of caregiving. A greater appreciation of strengths-based approaches in psychology mandates that we take a more holistic view of caregiving. Whereas there have been several studies exploring resilience among survivors of TBI, very little has been written about resilience in their caregivers. As with other types of illness, improving outcomes for persons with TBI may be predicated on the well-being of their support persons.^{231,232} Research to quantify and characterize the nature of caregivers' resilience postinjury is a cornerstone to advancing the evidence base on adjustment after TBI. Thus, the primary purpose of the proposed study is to investigate TBI caregivers' resilience over time. Understanding factors relating to resilience will likely help identify components of a resilience-building intervention for caregivers and ultimately help to improve outcomes for survivors.

B. Research Questions

For the past 30 years, we have had a strong interest in understanding and serving families after TBI. As clinicians, we have interviewed hundreds of caregivers and assessed their needs, concerns, and desires for resources. For the past 25 years, we have performed clinical research on family functioning, needs, life satisfaction, and emotional well-being with a focus on caregivers after TBI. For the past five years, we have been conducting research on resilience, focused on survivors. To develop the proposed module, we considered the comments and feedback from caregivers in our family practice. Further, the proposed module was also shaped by our Advisory Board, NDB participants, and NDB caregivers. Their feedback affirms that our new focus on caregiver resilience

is timely, relevant and complements our prior research. From our discussions, interviews and

review of the current literature, a series of important questions have emerged:

1.	What is the trajectory of caregiver resilience over the first two years postinjury? Does resilience
	change over time for some caregivers? If yes, what patient and caregiver factors are related to
	decline or improvement?
2.	What is the relationship between caregivers' resilience and their emotional well-being? Can the
	proposed longitudinal, multi-center study reproduce results from several single-center, small-
	sample studies with TBI and dementia caregivers?
3.	A few TBI caregiver studies found a relationship between caregiver resilience and perceived
	burden. In addition to perceived burden, do other caregiver factors (e.g., needs, time spent caring
	for the patient) relate to resilience?
4.	What is the relationship between caregiver resilience and patient characteristics, including
	resilience, emotional distress, and functional status?

C. Methodology

C1. Stage of Research

The proposed module project is best labeled as falling within the "Exploration and Discovery" stage of research. The present investigation is intended to generate hypotheses and theories through analysis of prospective, multi-center, longitudinal data. There is little information to aid our understanding of the construct of resilience in caregivers after TBI, despite the potential relevance to patients' rehabilitation and recovery. Research suggests that resilience can be improved with training, and we anticipate that the results of this project will facilitate the development of effective interventions that benefit caregivers and patients.

C2. Sample

Information regarding inclusion and exclusion criteria, enrollment rate, and participant incentives is provided herein. Recruitment information is provided in the *Procedure* section.

Inclusion criteria: Caregivers age 18 and older, identified within six months postinjury by TBIMS NDB participants (survivors) will be included. Participants will include relatives, friends, or other acquaintances involved in providing care, support, or other meaningful assistance to the survivor. In cases where there is more than one caregiver available, first priority will be given to the caregiver who is providing the most care to the survivor. A script will be developed for data collectors, allowing them to better identify a single caregiver for each survivor.

Exclusion criteria: Survivors who are unable to identify a relative, friend, or other caregiver will not be enrolled in the study. Formal caregivers, those who are a paid professional, will not be included in the study. Records will be kept indicating the number and type of exclusions. The data will be evaluated to help ascertain the representativeness of the final sample.

Enrollment rate: Considering the proposed eligibility criteria and past experience with similar research, we estimate accrual of no less than two caregivers per month, for a total of at least 26 annually. We anticipate three additional TBIMS centers will participate in this module with similar accrual rates. Conservatively, 78 VCU participants and 234 partner site participants will be enrolled for a total of 312 participants over the 36-month enrollment period. As noted in the *Data Analysis* section, the power analysis indicates our anticipated sample size is more than adequate.

Participant incentives: Caregiver participants will be given \$50 for completing each of the three assessments. Survivors will be given \$50 for completing the first assessment, as it falls outside of NDB protocol. Survivors will receive NDB protocol compensation (\$50) for the second and third assessments.

C3. Measures

The measures chosen for the present investigation were selected because they: (1) are relevant to project research questions; (2) have substantial evidence of reliability and validity; and (3) are included in the NDB.

Connor-Davidson Resilience Scale (CD-RISC): A full description of the CD-RISC can be found in the site-specific project (*Intervention to Promote Survivor Resilience and Adjustment* Measures section). As mentioned previously, normative studies including factor analyses indicated that the CD-RISC has excellent psychometric properties, including reliability, internal consistency, and construct validity.^{97,197,198} The scale has been effectively used with a wide variety of populations, including caregivers of relatives with Alzheimer's disease.^{229,233} The CD-RISC will be completed by both survivor and caregiver.

Patient Health Questionnaire-9 (PHQ-9): The PHQ-9 is used to assess depressive symptom severity and identify depression based on diagnostic criteria.²³⁴ The 9-item scale assesses frequency

of symptoms on a scale of "0" (not at all) to "3" (nearly every day). ²³⁴ Depression severity can be determined by calculating the total score, ranging from 0-27, with interpretation cut-off scores of 0-4 (minimal), 5-9 (mild), 10-14 (moderate), 15-19 (moderately severe) and >20 (severe).²³⁴ The PHQ-9 has good reliability and validity across clinical and racial/ethnic groups, including individuals with a history of TBI.²³⁴⁻²³⁶ This widely used measure of depression is also sensitive to change over time.²³⁷ The PHQ-9 will be completed by both survivor and caregiver.

Generalized Anxiety Disorder-7 (GAD-7): The GAD-7 is used to screen for generalized anxiety disorder and assess symptom severity.²³⁸ The 7-item scale is based on diagnostic criteria and review of existing measures.²³⁸ Frequency of symptoms are assessed on a scale of "0" (not at all) to "3" (nearly every day). Total scores range from 0-21, with increasing scores indicating more severe levels of anxiety.²³⁸ The GAD-7 is a reliable and valid measure of anxiety in the general population and in individuals with TBI.²³⁸⁻²⁴⁰ Both survivor and caregiver will complete the measure.

Family Needs Questionnaire (FNQ): The FNQ is a 37-item questionnaire developed to measure family members' perceived needs after a survivor's brain injury.²⁴¹ The items were designed to address diverse postinjury psychosocial and educational needs. Caregivers rate the degree to which each need has been met (not met, partly met, or met). An early investigation provided evidence of content and construct validity. Internal consistency was indicated by a Spearman-Brown split-half reliability of .75.²⁴² A later factor analytic investigation revealed six independent factors comprising six scales: Health Information, Emotional Support, Instrumental Support, Professional Support, Community Support Network, and Involvement with Care.²⁴³ Internal consistency for individual factors was indicated by Cronbach's alpha's ranging from 0.78 to 0.89. For the present investigation, the proportion of needs rated as met, converted to a 10-point scale, for the four scales most relevant to post-acute needs will be used (e.g., Emotional Support, Instrumental Support, Professional Support, Professional Support, Professional Support, Professional Support, Community Support Network).

Zarit Burden Interview (ZBI): The ZBI was originally developed as a 22-item questionnaire designed to quantify caregiving burden and is the most commonly used measure of such.²⁴⁴ Caregivers are asked to describe perceived changes in their emotional or physical health, social life,

and financial status as a result of caring for a relative. Items are rated on a 5-point Likert scale, ranging from 0 (never) to 4 (nearly always). A total score is derived, representing the extent of burden, with higher scores denoting greater burden. Research has evaluated the utility of a 12-item version.²⁴⁵ The correlations between the short and full version ranged from .92 - .97, substantiating the comparability of both versions. In a study among three caregiving populations (advanced cancer, dementia, and acquired brain injury), the 12-item ZBI had excellent validity (rho = .95-.97).²⁴⁶ Both the 12- and 22-item versions have been used with adult and pediatric TBI populations.^{66,219,223,247} The present investigation will utilize the 12-item version.

Caregiver demographics and history: Demographic data collected will consist of age, gender, race/ethnicity, marital status, household income, years of education, occupational status, and nature and length of relationship with survivor. To help characterize relationships, the caregiver will also be asked to indicate: (a) whether they are living with the survivor; (b) the number of hours spent caring for them daily; and (c) and the average number of days per week the caregiver sees the survivor. Additionally, information will be obtained about current and past mental health treatment and substance abuse, using the same variables as the NDB.

Survivor demographics and history: Data from the NDB protocol will be used. In addition, at the 6-month follow-up, the Disability Rating Scale and PART (Participation Assessment with Recombined Tools-Objective) will be collected.

Injury characteristics: The following information will be used from the NDB data collection: date of injury, etiology, admission GCS score, duration of unconsciousness and post-traumatic amnesia, duration of hospitalization, and history of neurosurgical intervention (e.g., craniotomy/craniectomy, ICP monitoring).

C4. Procedure

